16.2. Protocol Amendments

In accordance with ICH Topic E 6 (R1) Guideline for GCP the Investigator should not implement any deviation from, or changes of the protocol without agreement by the Sponsor and documented approval from the IRB/IECs of a protocol amendment, except where necessary to eliminate an immediate hazard(s) to study patients, or when the change(s) involves only logistical or administrative aspects of the study (e.g., change in monitor(s), change of telephone number(s)).

Any change to the protocol must be handled as a protocol amendment. Any potential amendment must be approved by the Sponsor. A written amendment must be submitted to the appropriate regulatory authorities and to the IRB/IECs assuming this responsibility. The Investigator must await IRB/IEC approval of protocol amendments before implementing the changes, except where necessary to eliminate apparent immediate hazard to patients. In these cases, the IRB/IEC must be notified within 5 days of the change.

All amendments to the protocol must be approved in writing by both the appropriate regulatory authorities and the IRB/IEC, except for administrative amendments, which require notification but not written approval. Once approved, the protocol amendment will be distributed to all recipients of the original protocol, with instructions to append the amendment to the protocol.

If, in the judgment of the local IRB/IEC, the Investigator, and/or Sponsor, the protocol amendment alters the study design, procedures and/or increases the potential risk to the patient, the currently approved written informed consent form will require modification. The modified informed consent form must also be reviewed and approved by the Sponsor, appropriate regulatory authorities, and the IRB/IEC. In such cases, repeat informed consent must be obtained from patients enrolled in the study before participation continues.

16.3. Protocol Adherence and Deviations

The protocol must be read thoroughly and the instructions must be followed. However, exceptions will be made in emergency situations when the protection, safety, and well-being of the patient requires immediate intervention based on the judgment of the Investigator or a responsible, appropriately trained, and credentialed professional(s) designated by the Investigator as a sub-Investigator.

In the event of a significant protocol deviation due to an emergency, accident, or error, the Investigator or designee must contact the Medical Monitor at the earliest possible time by telephone. This allows for an early joint decision to be made as to whether or not the patient

should continue in the study. The Investigator, the Sponsor, and the Medical Monitor will document this decision.

16.4. Publication Policy

After completion of the study, the Investigator(s) may prepare a joint publication with the Sponsor. The Investigator(s) must undertake not to submit any part of the data from this protocol for publication without the prior consent of the Sponsor.

16.5. Clinical Study Report

A final clinical study report will be prepared according to the ICH guideline on Structure and Contents of Clinical Study Reports. A final clinical study report will be prepared regardless of whether the study is completed or prematurely terminated.

16.6. Contractual and Financial Details

The Investigator (and/or, as appropriate, the hospital administrative representative) and the Sponsor will sign a clinical study agreement prior to the start of the study, outlining overall Sponsor and Investigator responsibilities in relation to the study. The contract should describe whether costs for pharmacy, laboratory, and other protocol-required services are being paid directly or indirectly. Financial Disclosure Statements will need to be completed, as requested by FDA CFR 21 part 54.

16.7. Insurance, Indemnity and Compensation

The Sponsor undertakes to maintain an appropriate clinical study insurance policy.

Deviations from the study protocol - especially the prescription of a dose other than that scheduled in the study protocol, other modes of administration, other indications, and longer treatment periods - are not permitted and shall not be covered by the statutory patient insurance scheme.

16.8. Discontinuation of the Study

This study may be terminated by the Sponsor. The study may also be terminated prematurely at any time when agreed to by both the Investigators and the Sponsor as being in the best interests of patients, and justified on either medical or ethical grounds. In terminating the study, the Sponsor, the CRO (PPD) and the Investigator will ensure that adequate consideration is given to the protection of the patients' interests.

16.9. Study Center File Management

The Investigator is responsible for assuring that the Study Center File is maintained. The Study Center File will contain, but will not be limited to, the information listed below:

1. Investigator's Brochure;
2. Current, signed version of the protocol and any previous versions of the protocol;
3. Protocol amendments (if applicable);

4. Operations Manual (if applicable);
5. Current informed consent form (blank) and any previous versions of the informed consent form;
6. Curricula Vitae of Investigator(s) and sub-Investigator(s) and photocopy of their respective license(s) where required by law; Original US FDA Form 1572 (for all studies conducted under US Investigational New Drug [IND] regulations), signed by all Principal Investigators. The names of any sub-Investigators must appear on this form. Investigators must also complete all regulatory documentation as required the ICH GCP and by local or national regulations;
7. Documentation of IRB/IEC approval of the protocol, the informed consent form, any protocol amendments, and any informed consent form revisions;
8. All correspondence between the Investigator, IRB/IEC, and the Sponsor/CRO relating to study conduct;
9. Lab certification(s);
10. Monitoring log;
11. Study drug invoices;
12. Signature list of all staff completing eCRFs; and
13. Signature list of all staff completing drug accountability summaries.

18. APPENDIX

18.1. Appendix 1: Elements of Informed Consent

ELEMENTS OF INFORMED CONSENT

Both the informed consent discussion and the written informed consent form and any other written information to be provided to patients should include explanations of the following:

- That the study involves research.
- The purpose of the study.
- The study treatment(s) and the probability for random assignment to each treatment.
- The study procedures to be followed including all invasive procedures.
- The patient's responsibilities.
- Those aspects of the study that are experimental.
- The reasonably foreseeable risks or inconveniences to the patient and, when applicable, to an embryo, fetus, or nursing infant.
- The reasonably expected benefits. When there is no intended clinical benefit to the patient, the patient should be made aware of this.
- The alternative procedure(s) or course(s) of treatment that may be available to the patient, and their important potential benefits and risks.
- The compensation and/or treatment available to the patient in the event of study-related injury.
- The anticipated prorated payment, if any, to the patient for participating in the study.
- The anticipated expenses, if any, to the patient for participating in the study.
- That the patient's participation in the study is voluntary and that the patient may refuse to participate or withdraw from the study, at any time, without penalty or loss of benefits to which the patient is otherwise entitled.
- That the monitor(s), the auditor(s), the IRB/IEC, and the regulatory authority(ies) will be granted direct access to the patient's original medical records for verification of clinical study procedures and/or data, without violating the confidentiality of the patient, to the extent permitted by the applicable laws and regulations and that, by signing a written informed consent form, the patient or the patient's legally acceptable representative is authorizing such access.
- That records identifying the patient will be kept confidential and, to the extent permitted by the applicable laws and/or regulations, will not be made publicly available. If the results of the study are published, the patient's identity will remain confidential.
- That the patient or the patient's legally acceptable representative will be informed in a timely manner if information becomes available that may be relevant to the patient's willingness to continue participation in the study.

1. INTRODUCTION

• ICH Guidance on Statistical Principles for Clinical Trials (E9)

2. PURPOSE OF ANALYSES

Holter monitors.

3. STUDY OBJECTIVES AND ENDPOINTS

3.1. Study Objectives

3.1.1. Primary Objective

The primary objective of the study is to compare the efficacy of RPC1063 vs. placebo for induction of clinical remission at Week 8 in patients with moderately to severely active ulcerative colitis (UC).

3.1.2. Secondary Objectives

The secondary objectives are to:

- Compare the efficacy of RPC1063 vs. placebo at weeks 8 and 32 as measured by clinical response, clinical remission, and mucosal healing
- Compare the overall safety and tolerability of RPC1063 vs. placebo for the duration of the study

3.1.3. Exploratory Objectives

3.2. Endpoints

3.2.1. Efficacy Endpoints

Primary Efficacy Endpoint:

[figure not shown]
• The primary endpoint is the proportion of patients in clinical remission at Week 8, defined as a Mayo score of ≤ 2 points and with no individual subscore of > 1 point

Key Secondary Efficacy Endpoints (rank ordered):

- Proportion of patients with a clinical response at Week 8, defined as a reduction from baseline in Mayo score of ≥ 3 points and ≥ 30%, and a decrease from baseline in the rectal bleeding subscore of ≥ 1 point or an absolute rectal bleeding subscore of ≤ 1 point
- Change from baseline in Mayo score at Week 8
- Proportion of patients with mucosal healing at Week 8, defined by an endoscopy subscore of ≤ 1
 point

Other Secondary Efficacy Endpoints:

- Proportion of patients in clinical remission at Week 32 defined as Mayo score of ≤ 2 points with no individual subscore of > 1 point
- Proportion of patients with a clinical response at Week 32, defined as a reduction from baseline in Mayo score of ≥ 3 points and ≥ 30%, and a decrease from baseline in the rectal bleeding subscore of ≥ 1 point or an absolute rectal bleeding subscore of ≤ 1 point
- Proportion of patients with mucosal healing at Week 32, defined by an endoscopy subscore of ≤ 1 point

3.2.2. Safety Endpoints

• The incidence and type of Adverse Events (AEs), Serious Adverse Events (SAEs), AEs leading to discontinuation of study treatment, target AEs of special interest, laboratory abnormalities, vital signs, electrocardiograms (ECG), and physical exam abnormalities

3.2.3. PK and PD Endpoints

- PK assessments will include PK sampling to determine plasma concentration of RPC1063 and active metabolites at scheduled assessments during the treatment period
- Absolute lymphocyte count (ALC) derived from blinded hematology laboratory results
- Plasma protein biomarkers (cytokines, chemokines, other inflammatory proteins)
- Stool analysis for fecal biomarkers fecal lactoferrin and calprotectin
- Total immunoglobulins (Igs) IgA, IgG, IgM

4. STUDY DESIGN

Study RPC01-202 is a Phase 2, multi-center, randomized, double-blind, placebo-controlled, parallel-group study in patients with moderately to severely active UC.

This study includes 3 periods (Screening, Induction, and Maintenance) and an optional Open-Label Treatment Period (OLP). Following the 5-week Screening Period, eligible patients will be randomized and enter the 8-week placebo-controlled Induction Period (IP). Patients who are responders at Week 8 will continue on their assigned treatment in the 24-week Maintenance Period (MP). Non-responders at Week 8 have the option to enter the OLP. Patients who complete the MP will be given the option to participate in the OLP. Patients that enter the MP and experience disease relapse will also have the option to enter the OLP.

The study will include both patients that have received anti-TNF therapy and those that have not. It is anticipated that approximately 50% of the patients included in the study will have received anti-TNF therapy.

The study design is shown in Figure 1.

Induction Period (IP)

The 8-week IP will serve as a dose-finding study to assess the efficacy and safety of RPC1063 for the induction of clinical response, remission, and mucosal healing in patients with moderately to severely active UC. The IP will actually last for 9 weeks and consists of dose titration over 8 days followed by the full dose for 8-weeks.

Approximately 180 patients will be randomized in a 1:1:1 ratio to receive 1 of 3 treatment regimens:

- RPC1063 0.5 mg oral capsule daily
- RPC1063 1.0 mg oral capsule daily
- Placebo oral capsule daily

The randomization will be stratified by prior anti-TNF therapy experience (yes or no).

For patients randomized to one of the active treatment groups, there will be an 8 day dose titration regimen in the IP consisting of 4 days of treatment with RPC1063 0.25 mg, followed by 3 days treatment with RPC1063 0.5 mg, followed by the assigned treatment level for approximately 8 weeks.

Maintenance Period (MP)

All patients who complete the IP and are responders at Week 8 of the IP will enter the 24-week MP. Patients will continue to receive the same study treatment in the MP as received during the IP, and individual patient treatment will remain blinded until all patients have reached Week 32. The last visit in

the MP will occur at Week 32. Patients who complete the MP will be given the option to participate in the OLP. Patients that enter the MP and experience disease relapse will have the option to enter the OLP.

Optional Open-Label Treatment Period (OLP)

Patients who complete the IP and are non-responders at Week 8 and those that complete the MP or experience disease relapse during the MP will have the option to enter the OLP. All patients in the OLP will receive daily study treatment with RPC1063 1.0 mg. There will be an 8 day dose titration regimen consisting of 4 days of treatment with 0.25 mg RPC1063, followed by 3 days treatment with RPC1063 0.5 mg, followed by RPC1063 1.0 mg. Patients who are non-responders 8 weeks after initiation of the OLP should discontinue from the study. The OLP will continue until the last patient who enters the OLP portion of the study has completed 20 weeks of treatment in the OLP.

[figure not shown]
Safety Monitoring/Follow-up

Potential adverse events (AEs) of interest that may be a consequence of sphingosine 1-phosphate 1 receptor 1 (S1P1R) modulation will be closely monitored during the study. These AEs include bradycardia and heart conduction abnormalities, pulmonary toxicity, macular edema, cutaneous malignancy, serious or opportunistic infection and hepatotoxicity. A Data Monitoring Committee (DMC) for the study will perform safety reviews periodically, approximately four times a year.

The safety of patients will be monitored by collection of treatment-emergent AEs, SAEs, physical exams, vital signs, Holter monitoring and ECGs, Pulmonary Function Tests (PFTs), optical coherence tomography (OCT), dermatologic exams, blood chemistry and hematology panels, coagulation panels, and urinalysis at baseline and at various time points during the study. White blood cell (WBC) counts and lymphocyte counts will be monitored centrally (and will not be provided to the site) to prevent potential unblinding of the Investigator.

Patients who discontinue from treatment due to lack of response, AEs, or other reasons, even if alternative treatment is given, will be followed for 30 days for collection of safety data, including lymphocyte recovery, and for the assessment of their disease status.

Figure 1: Study Schematic

5. **DEFINITIONS**

5.1. Time Point Definitions

Study Day for Induction and Maintenance Periods

All visit data will be assigned a study day, from the Visit 1 in the Induction Period according to the following rules:

- Visit 1 Day will be designated as Day 1
- All other days after Day 1: Study Day = (Visit Date Visit 1 Date + 1)
- All other days before Day 1: Study Day = (Visit Date Visit 1 Date)

Study days for evaluations occurring during the Screening visit will be negative numbers (e.g., "-7"), no Day 0 is defined for this study.

Study Day for the Open Label Period

All visit data will be assigned a study day, from the Visit 1 in the Open Label Period according to the following rules:

- OLP Day 1 will be designated as Day 1
- All other days after OLP Day 1: Open Label Day = (Visit Date Open Label Visit 1 Date + 1)
- All other days before OLP Day 1: Open Label Day = (Visit Date Open Label Visit 1 Date)

Baseline Measurement

There will be two baseline definitions:

Baseline: The latest assessments completed prior to initial study drug administration will be used as the Baseline measurement for all analyses for the IP and MP. It will also be used as the Baseline measurement for efficacy analyses for the OLP.

Treatment Baseline: The last assessment prior to initial administration of RPC1063 will be used as the Baseline measurement for safety analyses for the OLP.

Visits

Visits identifiers on the study electronic case report forms (eCRFs) will be used.

5.2. Efficacy Assessments

5.2.1. Flexible Sigmoidoscopy/Colonoscopy

To ensure quality data and standardization, the same endoscopist should be used throughout the study wherever possible. Colonoscopies will be read blinded to treatment allocation at a centralized reading facility, Robarts Clinical Trials.

5.2.2. Mayo Score

The Mayo score is a standardized, accepted, numerical scale used to evaluate disease severity in people with UC.

The Mayo score consists of four subscores, each ranging from (0-3) for a total score that ranges from 0 to 12:

- 1. Stool frequency^a
 - 0=Normal number of stools for this patient
 - 1 = 1 to 2 stools more than normal
 - 2=3 to 4 stools more than normal
 - 3=5 or more stools more than normal
- 2. Rectal bleeding^b
 - 0=No blood seen
 - 1 = Streaks of blood with stool less than half the time
 - 2=Obvious blood with stool most of the time
 - 3 = Blood alone passes
- 3. Findings on endoscopy
 - 0=Normal or inactive disease
 - 1 = Mild disease (erythema, decreased vascular pattern, mild friability)
 - 2 = Moderate disease (marked erythema, lack of vascular pattern, friability, erosions)
 - 3 = Severe disease (spontaneous bleeding, ulceration)
- 4. Physician's global assessment^c
 - 0 = Normal
 - 1 = Mild disease
 - 2 = Moderate disease
 - 3 = Severe disease

- ^a Each patient serves as his or her own control to establish the degree of abnormality of the stool frequency.
- ^b The daily bleeding score represents the most severe bleeding of the day.
- ^c The physician's global assessment acknowledges the three other criteria, the patient's daily recollection of abdominal discomfort and general sense of well-being, and other observations, such as physical findings and the patient's performance status.

The Mayo score will be derived at all visits when an endoscopy is performed. For these visits, the Mayo score will be derived using the endoscopy subscore and the non-endoscopy subscores performed at the same nominal visits, even if the assessments have different dates. The baseline Mayo score will be derived from the most recent endoscopy subscore (Item 3) completed during Screening and the last non-missing non-endoscopy subscores (i.e., Items 1, 2, and 4) prior to initial study drug administration.

Partial Mayo scores are calculated using data from Items 1, 2, and 4 only.

Mayo scores are calculated using:

- 1. The stool frequency and rectal bleeding data form the most recent consecutive 3-day period prior to the visit, excluding the following:
 - a. The day medications for constipation, diarrhea, or bowel irregularity are taken
 - b. The day(s) of a procedure or preparation for a procedure (e.g., enemas, other laxative, clear liquid diet) that would affect bowel frequency or blood content of the stool
 - c. The 48 hours following use of anti-motility agents (i.e., loperamide)
 - d. The 48 hours following endoscopy

Disease relapse is defined as when all of the following criteria are met:

- An increase in UC disease activity as defined by an increase in partial Mayo score of ≥2
 points compared to the Week 8 partial Mayo score with an absolute partial Mayo score ≥4
 points
- An endoscopic subscore of ≥ 2 points
- Exclusion of other causes of an increase in disease activity unrelated to underlying UC (e.g., infections, change in medication).

Using the full Mayo score:

Clinical Remission is defined as a Mayo score of ≤ 2 points and no individual subscore > 1 point Clinical Response is defined when all of the following criteria are met:

- Reduction in Mayo score of ≥ 3 points
- Reduction in Mayo score of $\geq 30\%$
- Reduction in Rectal Bleeding subscore of ≥ 1 point OR a Rectal Bleeding subscore of ≤ 1 point

Mucosal Healing is defined as an Endoscopic subscore of ≤ 1 point

Using the partial Mayo score:

Clinical Remission is defined as a partial Mayo score of ≤ 2 points and no individual subscore > 1 point Clinical Response is defined when all of the following criteria are met:

- Reduction in partial Mayo score of ≥ 2 points
- Reduction in partial Mayo score of $\geq 30\%$
- Reduction in Rectal Bleeding subscore of ≥ 1 point OR a Rectal Bleeding subscore of ≤ 1 point

5.3. Safety Definitions

AE or SAE Onset Date

AE and SAE onset or start dates are reported in the AE eCRFs.

AE or SAE End Date

AE and SAE end dates are reported in the AE eCRFs.

AEs and SAEs

AEs will be recorded from the time written informed consent is signed through the Follow-up visit (last dose + 30 days).

An AE or SAE will be regarded as treatment-emergent if it has a start date during or after the first study drug administration or if it worsened or if the relationship to study drug changed from unrelated to related after the first study drug administration. UC disease relapse and related symptoms will be monitored as study endpoints, but will not be recorded as AEs unless they meet the definition of an SAE.

All AEs or SAEs meeting these criteria with a start date up to and including 30 days following the last dose of treatment with the study drug will be considered treatment-emergent.

Treatment Related AEs

For summary purposes, all AEs classified by the Investigator on the AE eCRF as "possible", "probable" or "related" will be considered treatment related AEs. If the relationship to study drug is unknown or missing, the AE will be considered to be treatment related.

Duration of AEs

The duration of an AE will be calculated as:

Duration = (AE End Date - AE Onset Date) + 1

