12.1. Adverse Events

The AE definitions and reporting procedures provided in this protocol comply with current CFR 21 Part 312.32. An AE is any untoward medical occurrence that does not necessarily have a causal relationship with the investigational medicinal product. An AE can therefore be any unfavorable or unintended sign, including an abnormal laboratory finding, symptom or disease temporally associated with the use of an investigational medicinal product whether or not considered related to the investigational medicinal product.

UC disease relapse and related symptoms will be monitored as study endpoints, but will not be recorded as AEs.

AEs will be monitored throughout the entire study including the 90-day Safety Follow-up Visit. Investigators will ask the patient at each visit if they have experienced any untoward occurrence since the last study visit. All AEs will be recorded on the eCRFs provided: a description of the event, severity, time of occurrence, duration, any action (e.g., treatment and follow-up tests), and the outcome should be provided along with the Investigator's assessment of the relationship to the investigational drug.

AEs will be recorded from the time written informed consent is signed until 90 days following the last dose of treatment with the investigational drug.

If known, the event diagnosis should be recorded, in preference to the listing of individual signs or symptoms. AEs must be graded as being mild, moderate, or severe and their approximate duration given. Definitions of severity are as follows:

Mild: an AE usually transient in nature and generally not interfering with normal activities;

Moderate: an AE that is sufficiently discomforting to interfere with normal activities;

Severe: an AE that is incapacitating and prevents normal activities.

Even if the Investigator feels there is no relationship to the investigational drug, all AEs MUST be recorded in the eCRF. The Investigator is requested to assess the relationship of any AEs to treatment using the following definitions:

Unrelated: those AEs which are clearly and incontrovertibly due to extraneous causes (concurrent drugs, environment etc.) and do not meet the criteria for drug relationship listed under Unlikely, Possible, Probable or Related.

Unlikely: an AE may be considered unlikely if it includes at least the first two features:

- It does not follow a reasonable temporal sequence from administration of the drug.

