12.2. Serious Adverse Events

A SAE is any untoward medical occurrence or effect that fulfills the following criteria:

- Results in death
- Is life-threatening (NOTE: the term "life-threatening" refers to an event in which the patient was at risk of death at the time of the event; it does not refer to an event which hypothetically might have caused death if it were more severe)
- Requires hospitalization or prolongation of existing inpatient hospitalization

- Results in persistent or significant disability or incapacity
- Is a congenital abnormality/birth defect
- Important medical events not captured by the above but which may, for example, require medical intervention to prevent one of the outcomes above.

Medical and scientific judgment should be exercised in deciding whether expedited reporting is appropriate in other situations, such as important medical events that may not be immediately life-threatening or result in death or hospitalization but may jeopardize the patient or may require intervention to prevent one of the other outcomes listed in the definition above. These should also usually be considered serious. Examples of such events are intensive treatment in an emergency room or at home for allergic bronchospasm; blood dyscrasias or convulsions that do not result in hospitalization; or development of drug dependency or drug abuse.

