12.3. Reporting of Serious Adverse Events

Investigator reporting requirements for SAEs will be managed on behalf of the Sponsor by PPD. Full details of the procedures to be adopted will be documented in a safety management plan approved by responsible parties, in brief:

Any SAE which occurs to any patient from the time written informed consent is signed through the last visit must be reported by the Investigator. All SAEs that occur within 90 days of the last dose of treatment with the investigational drug, whether or not considered related to the investigational product, must also be reported. Any SAE that is ongoing when the patient completes the study or discontinues from the study will be followed by the Investigator until the event has resolved, stabilized, or returned to baseline status or the patient is lost to follow-up.

Any AE considered serious by the Investigator or Sub-Investigator or that meets serious criteria should be reported to PPD Pharmacovigilance (PVG) using the remote data capture (RDC) system. Data entry must be completed within 24 hours from the time the study site personnel first learned of the event.

In the event that RDC entry is not possible (e.g., system failure or access problems), the study site should complete the paper SAE report form and fax the form to PPD PVG within 24 hours of awareness of the event. The RDC system should be updated as soon as it is available.

Contact information for the PPD Pharmacovigilance Center:

SAE [contact]

SAE Fax line: [name]

The initial report should be promptly followed by detailed, written reports, which will include copies of hospital case records, discharge summaries, autopsy reports and other documents when requested and applicable. For unrelated cases, a full detailed case description may negate the need for additional hospital case records, discharge summaries, etc.

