6.20.1. Adverse Events

For presentation, adverse event verbatim text will be coded into MedDRA System Organ Class (SOC) and preferred term. For all AE summaries, if a patient has more than one AE within a preferred term, the patient is counted once in that preferred term at the maximum severity and closest relationship to study material or dosing procedure. If a patient has more than one AE within a system organ class, the patient is similarly counted once in that system organ class.

All AE safety summaries by treatment group will separately summarize the incidence of events in the placebo group, each RPC1063 dose group, and RPC1063 dose groups combined.

An overview of AEs will be tabulated by treatment group. The number and percentage of patients in each treatment group will be summarized for the following categories:

- any treatment-emergent AEs
- any SAEs
- treatment-related AEs
- •treatment-related SAEs
- •mild, moderate and severe AEs
- AEs with a start date during IP
- AEs with a start date during MP
- AEs with a start date during OLP
- AEs leading to study discontinuation
- AEs leading to study drug discontinuation

The following AE tables refer to AEs that are reported at any time during the study. The number and percentage of unique patients reporting each treatment-emergent AEs will be summarized by SOC, preferred term, and treatment group. A similar table will also be prepared separately for SAEs. Further, the number of treatment-emergent AEs and SAEs, categorized by SOC, preferred term, maximum severity (mild, moderate, or severe), and treatment group will be summarized. In addition, the number of treatment-emergent AEs and SAEs, categorized by system organ class, preferred term, relationship to study drug, and treatment group will be summarized. Finally, the incidence of AEs by preferred term only will be summarized, sorted by descending frequency in the combined RPC1063 group. All AE tables with both SOC and preferred term will be sorted by SOC alphabetically and then by preferred term in descending AE frequency in the combined RPC1063 treatment group. All of these AE and SAE tables will also be repeated for AEs that are reported with start dates during the IP, during the MP, and during the OLP.

AEs with start dates during a follow-up period will be categorized with the previous study phase.

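### Protocol 12.1 lacks the SAE exception that SAP 5.3 gives for UC relapse, so serious UC worsening may be captured inconsistently

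*SAP*

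**What the plan says.** Protocol 12.1 gives sites this rule: "UC disease relapse and related symptoms will be monitored as study endpoints, but will not be recorded as AEs". The sentence ends there, with no carve-out for serious events.

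SAP 5.3 repeats the rule but adds that these events "will not be recorded as AEs unless they meet the definition of an SAE". SAP section 8, which lists departures from the protocol, names only histologic remission and plasma protein biomarkers. It does not mention this difference.

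The protocol's SAE sections do not set UC events apart. Section 12.2 opens with "A SAE is any untoward medical occurrence or effect that fulfills the following criteria", and one of the criteria is "Requires hospitalization or prolongation of existing inpatient hospitalization". Section 12.3 states the general duty: "Any SAE which occurs to any patient from the time written informed consent is signed through the last visit must be reported". When 12.3 turns to how a report is made, the wording changes: "Any AE considered serious by the Investigator or Sub-Investigator or that meets serious criteria should be reported".

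On the analysis side, SAP 5.3 says that "AE and SAE onset or start dates are reported in the AE eCRFs". SAP 6.20.1 describes the table of treatment-emergent AEs by system organ class, preferred term and treatment group, then adds: "A similar table will also be prepared separately for SAEs". These tables are repeated for induction, maintenance and the open-label period.

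**The concern.** Sites work from the protocol, and the analysis works from the SAP. For a relapse that leads to hospital admission, protocol 12.1 taken alone says not to record it as an AE, while the SAP expects it among the SAEs. An event that a site never enters cannot be recovered by wording in the SAP.

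What is at stake is the completeness of the SAE tables. Serious worsening of the disease under study is a safety outcome. If some of the roughly 80 planned centres enter it and others do not, SAE incidence depends partly on how each site read the protocol. If serious relapse is more frequent in one arm, more events can be missing there and that arm looks safer than it was. The data monitoring committee's by-arm safety reviews (protocol 13.13) would be exposed to the same gap if they draw on the same records.

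**Working it through.** No arithmetic settles this. The check is to follow one case through each rule: a maintenance patient who meets the relapse definition and is admitted to hospital because of it.

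| Place | What it implies for this case |
|---|---|
| Protocol 12.1 | Not recorded as an AE |
| Protocol 12.2 | Admission is a seriousness criterion and UC is not excluded, so this is an SAE |
| Protocol 12.3, general duty | Must be reported |
| Protocol 12.3, reporting route | Open: it applies to a serious AE, and 12.1 has said that relapse is not recorded as one |
| SAP 5.3 | Recorded, because the SAE definition is met |

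**Within the protocol.** Sections 12.2 and the general duty in 12.3 point to reporting. Section 12.1 and the route wording in 12.3 leave room for the opposite. A careful site would probably report; a literal one might not.

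**Between the documents.** SAP 5.3 agrees with 12.2 and the general duty in 12.3. It conflicts with 12.1 as written.

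**Which periods are affected.** Disease relapse is a defined term (protocol 11.1.2, SAP 5.2.2). It needs a rise of at least 2 points over the Week 8 partial Mayo score, an absolute partial Mayo score of at least 4, an endoscopic subscore of at least 2, and exclusion of other causes. Since Week 8 is the reference, formal relapse cannot occur during induction. It can occur in maintenance, which only Week 8 responders enter, and protocol 10.6 also provides for relapse assessment in the open-label period. Protocol 12.1 goes further, however, and excludes *related symptoms*, which neither document defines. On a broad reading, a flare that leads to admission during induction is excluded too.

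**Route to the tables.** SAE dates come from the AE eCRF, and the SAE tables count what is there. Neither SAP 6.20.1 nor the open-label addendum (section 8) has a rule that identifies UC events or supplies them from another source.

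**Size.** The documents give no count or rate of serious relapses and no estimate of how sites would divide between the readings. For scale only: with about 60 patients per arm, one patient with an unrecorded SAE is 1/60 = 1.7 percentage points of that arm's incidence over the whole study. This is the weight of one patient, not an estimate of loss.

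**The case against.** The strongest reply is that the protocol, read as a whole, already reaches the SAP's position: 12.2 defines an SAE without excluding UC, and 12.3 requires any SAE in any patient to be reported. That stands. A reader might infer from 12.1 that serious relapse is never recorded; the SAE sections do not support that.

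A reader might also infer that the SAP's SAE tables cannot be produced as defined. They can be, from whatever SAEs are recorded. The risk is incompleteness.

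It is also not shown which wording sites followed. Full SAE procedures sit in a safety management plan that is not among the documents. The protocol and the main SAP text appear to date from different stages: the SAP body has a 30-day AE window, while the protocol and the open-label addendum have 90 days. An earlier protocol may have carried the exception; the documents do not say. This limits any claim about data already collected, but it does not reconcile the current texts.

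Serious worsening also leaves other traces. Colectomy or ostomy is a treatment-failure criterion (SAP 6.19), relapse has its own visit, and withdrawal reasons are tabulated by arm and period (SAP 6.11). These help, but they do not feed the SAE tables, and the addendum (section 7) applies no treatment-failure rule in the open-label period.

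Finally, no hypothesis tests are planned on safety data (SAP 6.20), so no p-value is affected. That is correct. The effect is on descriptive incidence and on how readers compare the arms.

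**Conclusion.** The inconsistency is real and should be removed. Protocol 12.1 omits an exception that SAP 5.3 states and that protocol 12.2 and 12.3 imply, and the route wording in 12.3 lets sites read the rules differently. Serious UC worsening may therefore be captured unevenly in the AE eCRF, leaving the SAE tables by arm incomplete. The exposure lies mainly in maintenance and the open-label period, and in induction only if *related symptoms* is read broadly.

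The size cannot be derived. Saying that capture could lie anywhere from none to all only restates that two readings exist. The direction of any bias is not fixed either: it depends on which arm has more serious relapses, and in maintenance also on how many responders each arm contributes.

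The conclusion assumes that at least some sites worked from 12.1 as it now reads and that no other instruction told them to enter serious relapses. The documents neither confirm nor exclude this. The primary efficacy analysis is not affected.

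**What to change.** Reconcile the passages by adding to protocol 12.1 the exception that SAP 5.3 already states: UC relapse and related symptoms stay out of AE recording unless they meet an SAE criterion, in which case they are recorded and reported as SAEs under 12.3.

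For data already collected, state in the clinical study report which rule sites followed and how serious UC events were captured, and show SAE incidence by arm with and without UC terms. The preferred-term tables in SAP 6.20.1 let a reader pick out individual UC terms, but they do not give the number of patients with any SAE once those terms are removed.

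The cost is one protocol sentence, a few more SAE reports and one extra table. The change concerns recording and reporting only.
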